- 338 8. Randomization of newly enrolled subjects and previously enrolled conventional care subjects to
339 a second biopsy after 1, 2, or 4 years of HPTH therapy. A dynamic allocation scheme will be
340 used to ensure balance across biopsy arms by gender, menopausal status, and prior participation
341 in the protocol (see Section 10.3). The principal investigator or designee will perform the
342 randomization procedure using a secure, web-based randomization system.

343 All subjects will receive HPTH at a starting dose of 0.2 µg/kg/dose subcutaneously twice a day. After the
344 initial dosing, HPTH will be titrated based on serum calcium levels, according to the dosing algorithm in
345 Appendix 24.10. Each subject will receive education and written materials about HPTH administration
346 and dosing adjustment prior to discharge (Appendix 24.11). The drug will be provided to all subjects free
347 of charge. The NIH Clinical Center Pharmaceutical Development Service (PDS) will be responsible for
348 labeling, storing, preparing, dispensing, and maintaining accountability records for HPTH.

349 **4.5.3 Follow-up Visits During HPTH Therapy**

350 Subjects will be seen at the NIH every 6 months (± 2 weeks) until they have completed up to 5 years of
351 HPTH therapy. The second biopsy will occur at one of these visits, with the timing of that biopsy
352 determined by random assignment. Subjects currently on HPTH therapy under the previous version of the
353 protocol will be re-consented at the first follow-up visit they attend. Follow-up visits may be conducted
354 on an inpatient or outpatient basis at the discretion of the investigator, except for biopsy visits which must
355 be inpatient. Follow-up visits will last 1-3 days if a biopsy is not being performed and 5-7 days if a biopsy
356 is being performed. Additional visits may be scheduled at the discretion of the investigator in order to

357 assess adverse events or other problems that may arise. All subjects will undergo the procedures and tests
358 described below at each follow-up visit, unless otherwise noted:

359 1. History

360 a. Detailed history of current disease and adverse events

361 b. Current medications

362 c. Dietician consultation

363 d. Short Calcium Questionnaire (Appendix 24.5)

364 e. SF-36 Health Survey (Appendix 24.7).

365 2. Fitness measures

366 a. Fatigue Symptom Inventory (Appendix 24.8)

367 b. 6-Minute Walk Test (Appendix 24.9)

368 3. Physical Exam

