369 a. Height and weight measurement

370 b. Vital signs (pulse, blood pressure, temperature, and respiratory rate)

371 c. Physical examination

372 4. Blood tests

373 a. Blood chemistries: sodium, potassium, chloride, bicarbonate, creatinine, glucose, urea
374 nitrogen, albumin, calcium, magnesium, phosphorous, alkaline phosphatase, ALT, AST,
375 total bilirubin, direct bilirubin, LD, total protein, total CK, and uric acid

376 b. TSH and Free T4

377 c. 25-OH vitamin D, 1,25 (OH)₂ vitamin D, intact PTH

378 d. CBC: WBC, RBC, hemoglobin, hematocrit, MCV, RDW, and platelets

379 e. Research bloods for storage and potential future use (as yet undetermined)

380 f. Mineral panel or calcium level (performed and repeated as needed): albumin, calcium,
381 magnesium, phosphorous

382 g. Bone-specific alkaline phosphatase

383 h. Osteocalcin

- 384 i. Ionized calcium
- 385 j. Twenty-four hour blood sampling: Every 2-hour \pm 15 min sampling (for 24 hours) for calcium,
386 magnesium, phosphorus, and albumin will be done after 1 year on PTH. An IV catheter or PICC
387 line may be placed for convenience of drawing blood during this inpatient visit.
- 388 5. Urine testing
- 389 a. Urine pregnancy test in females with childbearing potential
- 390 b. Urinalysis: glucose, protein, urobilinogen, pH, hemoglobin, ketones, nitrite, leukocyte
391 esterase, appearance, specific gravity, color, RBC, WBC, and squamous cells
- 392 c. Two 24-hour urine collections for testing of calcium, phosphorus, creatinine, magnesium,
393 sodium, citrate, N-telopeptide, pH, and potassium
- 394 6. Imaging - to be done at the start of PTH therapy and then annually (with the exception of the
395 DXA)
- 396 a. Renal ultrasound to assess the presence of nephrocalcinosis
- 397 b. CT of the kidney without contrast to assess the presence of nephrocalcinosis
- 398 c. DXA scan of the spine, femur, radius and total body – every visit to assess bone density
- 399 d. Quantitative CT of the L1 and L2 spine to assess bone density
- 400 7. Second and final bone biopsy at one of the visits (see Section 4.5.6)

401 **4.5.4 Outpatient Blood and Urine Collections**

402 All subjects will be given a laboratory slip to be used at their local laboratory for measurement of serum
403 calcium and 24-hour urine calcium, sodium, and creatinine. Subjects will be instructed to obtain blood
404 tests at least once a week (\pm 2 days) immediately after starting PTH therapy. After 4 consecutive serum

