405 calcium levels within the target range, subjects will be instructed to obtain blood work a minimum of
406 once a month (\pm 1 week). Urine collections should be obtained approximately every 3 months (\pm 2
407 weeks). Additional outpatient blood or urine tests may be ordered as clinically indicated. Participants will
408 be instructed to have lab results sent to the research team. The principal investigator or designee will
409 review the results of these tests, adjust medication doses, and order additional testing according to the
410 HPTH dosing algorithm (Appendix 24.10). Prior to making any dose adjustment decision, the investigator
411 will assess the subject's adherence to medication instructions. The investigator will record all dosing
412 decisions, along with the laboratory values associated with those decisions.

413 **4.5.5 *Monitoring of Calcium-Citrate Ratio and Concomitant Potassium Citrate***

414 All subjects will be monitored for hypocitraturia during the inpatient visits. As hypocitraturia may
415 increase the risk of renal calcifications, subjects with a urinary calcium/citrate ratio greater than 0.7 will
416 receive potassium citrate supplementation, in attempt to lower this ratio. It should be noted that complete
417 normalization of the urinary citrate excretion and reduction of the calcium/citrate may be impossible in
418 these subjects, due to chronic renal tubular dysfunction associated with this disease. Urinary citrate and
419 pH will be monitored on the outpatient collection, as well as during the NIH visits, in subjects treated
420 with potassium citrate. If the urinary pH rises above 7, adjustments to potassium citrate dosing may be
421 made after consultation with the nephrologist on the study team.

422

423 **4.5.6 *Bone Biopsy Procedures***

424 Two percutaneous transiliac crest biopsies will be performed after antibiotic labeling, with one biopsy
425 performed prior to HPTH therapy and the second during HPTH therapy. The biopsy will be performed by
426 a licensed practitioner credentialed in this procedure in the operating room of the NIH Clinical Center
427 under local anesthesia with sedation. The baseline and second biopsy will be obtained from opposite
428 sides. Subjects will be pre-treated with either tetracycline or demeclocycline. Tetracycline will be
429 delivered according to the following schedule: 3 days of tetracycline (250 mg 4 times per day), 12 days

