725 for evidence of AEs. Events will be followed until they return to baseline, until follow-up is no longer
726 medically necessary, or until the end of the AE surveillance period.

727 The following conditions will require the withdrawal of a subject from the HPTH therapy:

- 728 • Pregnancy
- 729 • New-onset illness requiring chronic use (> 3 weeks) of a medication that affects the bone such as
730 oral glucocorticoids, growth hormone, suppressive doses of thyroid hormone, estrogen or
731 testosterone. Inhaled, topical, and intranasal glucocorticoids are permitted.

- 732 • Women who enter menopause after initiation of HPTH therapy will not be withdrawn from the
733 study unless they require hormone replacement therapy for > 3 weeks.
- 734 • Use of depot medroxyprogesterone for contraception. Subjects wishing to use oral, transdermal,
735 intravaginal, or intrauterine hormonal contraceptives may remain in the study.
- 736 • Significant deterioration in metabolic control on PTH as defined by repeated measurements of
737 serum calcium < 7 mg/dL for more than 4 weeks.
- 738 • Severe chronic bone pain or other unexpected new-onset chronic medical condition that cannot be
739 explained and may be related to PTH therapy
- 740 • Development of DXA or QCT Z-Score or T-score < -2. As peak bone mass is not achieved until
741 the third decade of life, subjects beginning PTH before age 20 will only have Z-score assessed for
742 withdrawal determination.
- 743 • Decline in calculated GFR of < 25 mL/min/1.73 m² or decline in calculated GFR by 25
744 mL/min/1.73m² without clear etiology that persists on three monthly measurements (measured at
745 the NIH or the subject's local laboratory).
- 746 • Increase in hepatic transaminases (ALT and AST) > 2x the upper limit of normal
- 747 • Treatment failure as defined by significant metabolic deterioration
- 748 • Recurrence of thyroid cancer in subjects with history of thyroid cancer
- 749 • Subject noncompliance with study procedures.
- 750 • Investigator judgment based on subject's best medical interest

751 Subjects who require discontinuation of HPTH therapy will be gradually weaned off HPTH while
752 therapeutic doses of calcitriol and calcium are established as described in Section 4.5.5.

753 **9 OUTCOME MEASURES**

754 **9.1 Primary Outcome Measures**

755 The primary outcomes are changes in static and dynamic bone histomorphometry after 1 year, 2 years,

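### Add serum creatinine to the monthly local draw: the GFR that the Section 8 withdrawal rule needs is routinely scheduled only at 6-monthly NIH visits

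*Protocol*

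**What the plan says.** **Local tests (Protocol 4.5.4).** Subjects receive a slip for serum "calcium and 24-hour urine calcium, sodium, and creatinine. Subjects will be instructed to obtain blood" tests weekly at first, then at least monthly once four consecutive calcium values are in range. "Urine collections should be obtained approximately every 3 months", and "Additional outpatient blood or urine tests may be ordered as clinically indicated".

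**NIH visits (4.5.3).** "Subjects will be seen at the NIH every 6 months", with a 2-week window. The panel at each visit includes serum creatinine: "Blood chemistries: sodium, potassium, chloride, bicarbonate, creatinine, glucose, urea". An unscheduled visit is also possible: "Additional visits may be scheduled at the discretion of the investigator in order to" assess adverse events or other problems.

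**Withdrawal rule (Section 8).** HPTH stops on "Decline in calculated GFR of < 25 mL/min/1.73 m² or decline in calculated GFR by 25" mL/min/1.73 m² "without clear etiology that persists on three monthly measurements (measured at" the NIH or the subject's local laboratory). The CKD-EPI equation is named in the exclusion criteria (3.3).

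**Dosing algorithm (Appendix 24.10).** The only laboratory value it uses or asks to be rechecked is serum calcium.

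**The concern.** The GFR criterion is the only numeric renal criterion in the Section 8 list. It speaks of monthly values and accepts local laboratory results, yet no section schedules a local serum creatinine that would give the first signal. Urine creatinine alone does not yield a CKD-EPI GFR. Urine calcium, the calcium/citrate ratio and annual imaging follow the cause of damage and calcification, not filtration.

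What is at stake is patient safety, not the primary analysis. The Introduction names renal insufficiency or failure as a possible result of chronic hypercalciuria. Section 7.10.4 says the renal risk linked to hypocitraturia in these patients is unknown. Subjects may enter with a GFR as low as 25. The appended teriparatide label reports AUC higher by 73% in 5 patients with creatinine clearance below 30. A fall in GFR can go unmeasured for up to half a year although blood is already drawn at least monthly.

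**Working it through.** The documents state no detection time, so there is no planned figure to reproduce.

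**Inputs from the protocol:** NIH visits every 6 months, window 2 weeks either side; local blood at least monthly, window 1 week either side.

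**Assumptions, not in the documents:** onset uniform within the test interval; fall abrupt and lasting; every scheduled test attended; no measurement error; no discretionary test.

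**1. Delay to the first value that can show the fall.** Mean = interval/2.

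| | As written | Monthly creatinine |
|---|---|---|
| Mean, months | 6/2 = 3.0 | 1/2 = 0.5 |
| Mean, windows simulated | 3.02 | 0.52 |
| 90th percentile, simulated | 5.4 | 0.96 |
| Worst case, windows included | 6 months + 4 weeks = 6.9 | 1 month + 2 weeks = 1.5 |

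The mean gain is 2.5 months; the 10th to 90th percentile of the gain per onset is 0.1 to 4.9 months.

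**2. Relaxing the assumptions.** If only 80% of monthly draws are done, the mean with the change is about 0.7 month; at 50% it is about 1.2. With an assumed GFR error SD of 3 to 8 per measurement and a true fall of 30, the means are 3.8 to 5.9 months as written and 0.6 to 1.0 with the change.

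**3. Gradual decline.** Further GFR lost at the mean delay = yearly rate × delay/12.

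| Assumed rate, mL/min/1.73 m² per year | As written | Monthly | Gain |
|---|---|---|---|
| 5 | 5 × 3.0/12 = 1.25 | 5 × 0.5/12 = 0.2 | 1.0 |
| 10 | 2.5 | 0.4 | 2.1 |
| 25 | 6.25 | 1.0 | 5.2 |

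**4. From first value to withdrawal.** On the decline-by-25 limb, three monthly values add about 2 months under either schedule: 3.0 + 2 = 5.0 against 0.5 + 2 = 2.5. The gain stays at 2.5 months if the first value starts monthly confirmation.

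On the < 25 limb the wording is unclear, because the persistence clause follows the second limb.
- If one value below 25 now suffices, mean time to withdrawal is 3.0 months. Monthly testing plus three monthly values would take 0.5 + 2 = 2.5, a gain of only 0.5 month. The chance that withdrawal comes later than now is P(U(0,6) < U(0,1) + 2) = 2.5/6, about 42%.
- If persistence already covers this limb, mean time is now about 5.0 months.
- A repeat 1 to 2 weeks (0.23 to 0.46 month) after a low local value gives 0.5 + 0.23 to 0.5 + 0.46, or 0.7 to 1.0 month. This is earlier on average than either reading.

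**5. Chance low values.** Assume a within-person CV of 8%, independent values and a stable GFR of 30. The SD is 2.4 and P(value < 25) = P(Z < −5/2.4) = 0.0186. Expected low values in 60 tests: 60 × 0.0186 = 1.1. The chance of at least one is 17% in 10 visits and 68% in 60 monthly tests (0.4% and 2.5% at CV 5%; 39% and 95% at CV 10%). Requiring the repeat to be low too gives 60 × 0.0186² = 0.02 expected confirmed false alarms. At CV 10% (SD 3, P = 0.048) it is 60 × 0.048² = 0.14. Repeats close in time may be correlated, which would raise these figures.

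**The case against.** Six-monthly GFR with discretionary testing is a defensible choice. Extra local tests and visits are allowed, Section 8 already accepts local GFR values for confirmation, urine is collected about quarterly, renal imaging is annual, and a nephrologist is on the team. The harm cited comes from chronic hypercalciuria, which suggests slow loss, where the gain of about 1 to 2 mL/min/1.73 m² is below the assumed measurement SD (2.4 at a GFR of 30). No document gives the rate of fast falls, so the expected benefit cannot be quantified. Monthly testing without a confirmation step would also raise the number of chance low values.

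Most of this stands and limits the point to a low-cost improvement. It does not remove it: a discretionary test needs a prompt, and no routine between-visit test measures filtration.

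A reader might infer that the withdrawal rule cannot be operated, or that local creatinine was never measured. The documents do not support either. The discretionary routes exist, and neither the laboratory slip nor the discharge instructions (Appendix 24.11) could be examined, so the point rests on the text of 4.5.4. A reader might also think that three monthly values should be required on both limbs to control false alarms. Step 4 shows why not: if one value below 25 now suffices, that would loosen the renal stop.

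**Conclusion.** The point holds as an inexpensive safety improvement. Section 4.5.4 names serum calcium as the only routine local blood analyte, so a GFR for the Section 8 rule is scheduled only every 6 months unless someone orders it. Under the assumptions in the working, the first informative value comes 2.5 months sooner on average. That advantage survives missed draws and measurement noise, but it matters mainly for fast falls.

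It would go too far to claim better renal outcomes: the documents do not show that earlier withdrawal changes them. The remaining benefit is also limited by timing. SAP Section 9 says weaning began when enrollment ended in June 2015, and this protocol version is dated September 2015. That reduces the benefit and the cost alike.

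**What to change.** 1. In 4.5.4 and on the slip, add serum creatinine with a calculated CKD-EPI GFR to the monthly local draw. It is not needed on each early weekly draw. If the slip already includes it, 4.5.4 should say so.
2. In Section 8, state that a local value below 25 triggers a prompt repeat, for example within 1 to 2 weeks, before withdrawal. Keep the three-monthly-measurements requirement on the decline-by-25 limb only. The investigator-judgment criterion still allows immediate withdrawal.

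**Cost.** One sentence in 4.5.4, one clause in Section 8, and one routine assay per subject per month on blood already drawn: 12 × 5 = 60 over a full 5-year course. There is no added scheduled visit or routine venepuncture; only a triggered repeat needs another draw. Expect some repeats after chance low values, mainly in subjects with GFR near 25 to 30, and some differences between local and NIH assays, for which the documents give no figure. Eligibility, dose, visit schedule and endpoints stay the same.

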675 **7.10.4 Adverse Events**

676 The safety of parathyroid hormone replacement therapy has been demonstrated in clinical trials involving
677 the treatment of hypoparathyroidism and osteoporosis. In a long-term NIH study comparing HPTH to
678 conventional care for the treatment of hypoparathyroidism, there were no significant differences between
679 treatment groups in the incidence of most adverse events, such as neuromuscular irritability, fatigue, or
680 arthralgias.⁵ Mild intermittent bone pain in the lower extremities occurred in 7 subjects receiving HPTH
681 and in 3 subjects receiving conventional care. The most common adverse events (>10% of subjects)
682 observed in clinical trials of rhPTH for osteoporosis included arthralgia, pain, and nausea. Another
683 common adverse event in these trials was the development of hypercalcemia. In this study, an increase in
684 serum calcium is a desired pharmacologic effect and would not be considered an AE, unless serum
685 calcium > 11 mg/dL persisted for more than 4 weeks. Transient orthostatic hypotension has been
686 infrequently observed in subjects treated with rhPTH for osteoporosis. This event typically occurred
687 within 4 hours of dosing and resolved spontaneously.¹⁸ Additional information about other adverse events
688 is available in the Forteo® package insert (Appendix 24.13).

689 Resistance to PTH and anti-PTH antibodies have been reported in 3% of women treated with rhPTH.¹⁸ In
690 patients with hypoparathyroidism, PTH resistance would manifest by diminishing responsiveness to the
691 therapy that will require increasingly greater doses of PTH to maintain normal serum calcium. Among the
692 subjects who develop resistance, many will be able to continue therapy if the resistance is small or partial.
693 Others may develop substantial resistance with unstable serum calcium and phosphate levels. PTH
694 therapy will be discontinued in those subjects, and those subjects will be withdrawn from the study after
695 returning them to conventional therapy (see Section 4.6).

696 Decreases in BMD of the radius, as measured by DXA, have been noted in preliminary data from this
697 protocol²⁵ and other studies treating hypoparathyroid subjects with HPTH⁵ and PTH 1-84¹⁰.

698 Histomorphometric analysis has also shown an increase in cortical porosity^{11,25,26}. Decreases in radial
699 BMD have been reported in euparathyroid postmenopausal women treated with rhPTH 1-34 without an

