700 apparent increase in wrist fractures¹² or change in cortical porosity¹⁴. The clinical relevance of these
701 changes in radial BMD in hypoparathyroid treated with HPTH is unknown. Thus, this protocol excludes
702 and withdraws subjects with DXA BMD T-scores or Z-scores < -2.

703 Since this study has started, hypocitraturia (defined as a urine calcium to citrate ratio > 0.7 mg/mg) has
704 been observed in many subjects initiation of HPTH therapy. Of note, some subjects also had elevated
705 urine calcium/citrate ratios prior to the initiation of HPTH. Hypocitraturia has not been previously
706 reported in hypoparathyroidism and, to our knowledge, urine citrate has not been assessed in other studies
707 using PTH 1-34 or PTH 1-84 in the treatment of hypoparathyroidism. Thus, the risk of hypocitraturia-
708 associated nephrocalcinosis or nephrolithiasis in this patient population, on conventional or PTH therapy,
709 is not known. The urine calcium/citrate ratio will be monitored throughout the study and subjects will be
710 treated with potassium citrate, as tolerated, as described in section 4.5.5.

711 There is a risk of unforeseen adverse effects with every new drug treatment. The risks of participation are
712 reasonable relative to the significant health benefits and medical knowledge that may be achieved.

713 **8 SUBJECT SAFETY MONITORING**

714 Subjects will be informed that they may choose to withdraw or the investigator may remove them if it is
715 in the subjects' best interest or if the subjects are unable to complete the required assessments. Voluntary
716 withdrawal from the protocol is always an option for the research participants. As described throughout
717 Section 4.5, subjects will have blood and urine measured and evaluated by the study investigators on an
718 ongoing basis, and HPTH dosing will be adjusted according to a standardized dosing algorithm. The
719 principal investigator or designee will evaluate all clinical laboratory results for clinically significant
720 abnormalities and document the evaluation on a CRF. Clinically significant laboratory findings will be
721 recorded and reported as AEs (see Appendix 24.1) regardless of their association with the use of the
722 investigational product.

723 At each study visit, the study investigator will inquire about the occurrence of any AEs since the last visit.
724 The principal investigator will also review all source documentation related to inpatient study procedures

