1 DEFINITIONS

1.1 Adverse Event

An AE is any untoward medical occurrence in a human subject, including any abnormal sign (for example, abnormal physical exam or laboratory finding), symptom, or disease, temporally associated with the subject's participation in research, whether or not considered related to the subject's participation in the research. In the context of FDA reporting, an AE means any untoward medical occurrence associated with the use of a drug in humans, whether or not considered drug related.

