3.2 Clinically Significant Laboratory Abnormalities

The principal investigator will evaluate all clinical laboratory results for clinically significant abnormalities and document the evaluation in a CRF. Clinically significant findings (e.g., increase in calcium-citrate ratio to >0.7) will be recorded and reported as AEs regardless of their

association with the use of the investigational product. The principal investigator will follow significant abnormalities until they return to baseline or stabilization.

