24.10 Dosing Algorithm

PTH Dosing Algorithm

Serum Calcium Level	Dose Titration
< 6.0 mg/dL < 1.5 mmol/L	
 • Calcium 1000-1800 mg PO as a single dose. • Refer to the Emergency Department for calcium infusion • Increase PTH dose by 20-50% • Check serum calcium within 2 – 3 days
6.1 to 6.9 mg/dL 1.52 to 1.73 mmol/L	
 • Increase PTH dose 10 to 20% • Calcium 1000mg to 1800 mg PO as a single dose • Check serum calcium within 2 – 3 days
7.0 – 7.5 mg/dL 1.75 – 1.88 mmol/L	
 • Increase PTH dose 5 to 20% and/or Calcium 500 – 1200 mg PO as a single dose • Check serum calcium at least once within a week of dosing change
7.6 – 9.0 mg/dL 1.9 – 2.25 mmom/L	
 • No change or 5% increase/decrease in PTH dose or increase/decrease in calcium supplements • Check serum calcium at least once a month • If change in dose was made, recheck calcium within one week
9.1 – 10.9 mg/dL 2.28 – 2.73 mmol/L	
 • Decrease PTH dose 5 to 20% and/or decrease oral calcium supplements • Check serum calcium once a week until calcium level is back to target range.
11.0 - 11.9 mg/dL 2.75 – 2.98 mmol/L	
 • Temporarily suspend PTH dosing and calcium supplements • Check serum calcium within 2 – 3 days • Resume PTH dosing, decreased 20-40 % when serum calcium < 11.0 mg/dL, 2.75 mmol/L
> 12.0 mg/dL > 3 mmol/L	
 • Temporarily suspend dosing and calcium supplements • Refer to the Emergency Department for IV fluids • Check serum calcium within 2 – 3 days • Resume dosing, decreased 20-40 % when serum calcium < 11.0 mg/dL, 2.75 mmol/L

Prior to any change in PTH dose, subject compliance, symptoms, and general state of health must be assessed by a member of the protocol team.

If the current dose of PTH is < 5 mcg/dose, PTH will be adjusted at the investigator's discretion.

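### The only related-AE table in the SAP includes events the protocol classes as not related, and the protocol leaves unsettled whether hypercalcaemia that stops dosing is an AE

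*Protocol*

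**What the plan says.** **Relatedness.** Protocol Appendix 24.1 section 2.2 sorts causality grades into two groups. Possible, probable and definite are related; not related and unlikely are not related. SAP section 10 lists one AE table by relationship to hPTH, and its title puts Unlikely on the related side with the other three grades. SAP section 1 says the safety analyses have already gone to the DSMB. SAP section 8 carries those tables forward and allows further safety tables if the PI asks for them.

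**Hypercalcaemia.** Four places in the protocol bear on it.

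- Section 7.10.4: a rise in "serum calcium is a desired pharmacologic effect and would not be considered an AE, unless serum" "calcium > 11 mg/dL persisted for more than 4 weeks".
- Section 8: laboratory findings judged clinically significant are to be "recorded and reported as AEs (see Appendix 24.1) regardless of their association with the use of the" study product.
- Appendix 24.1: section 1.1 defines an AE as an untoward occurrence, "including any abnormal sign (for example, abnormal physical exam or laboratory finding), symptom, or disease". Section 3.2 says clinically significant findings "will be recorded and reported as AEs regardless of their" link to the product. Its one example is a raised calcium-citrate ratio; serum calcium is neither named nor exempted.
- Appendix 24.10: the 11.0–11.9 mg/dL row says "Temporarily suspend PTH dosing and calcium supplements". The row above 12.0 mg/dL also stops dosing and adds "Refer to the Emergency Department for IV fluids". Both ask for a recheck within 2–3 days. The restart instruction is "Resume PTH dosing, decreased 20-40 % when serum calcium" is below 11.0 mg/dL.

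Protocol section 17 lets NIH SOP 16 prevail where there is a discrepancy. That SOP is not among the documents.

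**The concern.** Both points affect what a reader of the AE tables will take the counts to mean.

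A count headed as related will be read as the protocol's related count. It is larger by every event graded Unlikely, and no other listed table supplies the narrower figure.

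For calcium, two rules can give different AE counts from the same episodes. Under 7.10.4 alone the count can be zero however many suspensions there were, if each resolved within 4 weeks. Under section 8 and Appendix 24.1 section 3.2 it depends on the investigator's judgement of clinical significance. The choice carries further: Appendix 24.1 section 1.2 defines an SAE as a kind of AE, and the second halting rule in protocol section 15.3 counts AEs and SAEs. Apart from AE counts, the listed chemistry summaries cover only the experimental time-points (baseline, last hPTH treatment and follow-up in SAP section 10; SAP 7.4.2.4 adds month 6). No listed table counts high values between visits.

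**Working it through.** The plan gives no figure to reproduce, so the check compares the texts.

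**1. Relatedness categories**

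- Protocol related (Appendix 24.1 section 2.2) = {Possible, Probable, Definite}.
- SAP related (section 10 table title) = {Unlikely, Possible, Probable, Definite}.
- SAP count = protocol count + events graded Unlikely.

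The SAP table therefore contains every protocol-related event and never falls short. The excess cannot be computed, because the documents do not report how many events were graded Unlikely.

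**2. Calcium episodes under each rule (no symptoms)**

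| Episode | Appendix 24.10 action | Section 7.10.4 alone | Section 8 and Appendix 24.1 section 3.2 |
|---|---|---|---|
| In the 11.0–11.9 row, below 11.0 at the 2–3 day recheck | hPTH and calcium supplements stopped | Not an AE | AE if judged clinically significant |
| Above 12.0, below 11.0 at the 2–3 day recheck | Both stopped, plus emergency referral | Not an AE | AE if judged clinically significant |
| Above 11 for more than 4 weeks | Both stopped until below 11.0 | AE | AE if judged clinically significant |
| Exactly 11.0, any duration | Both stopped | Never an AE (needs above 11) | AE if judged clinically significant |

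The rules can part company in the first, second and fourth rows.

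**3. How demanding the 4-week test is**

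- 4 weeks = 28 days = 28 × 24 = 672 h.
- The algorithm rechecks within 2–3 days. It does not say that this repeats. Assuming it does while calcium stays at 11.0 or above, 28/3 = 9.3 and 28/2 = 14, so about 9 to 14 successive rechecks would fall in the period.
- Protocol section 6.1.2 has the drug unquantifiable within 3 h of injection, and section 6.1.3 puts the calcium peak at 3–4 h in NIH experience. A rise caused by hPTH and managed by the algorithm would be expected to settle well before 672 h. Hypercalcaemia from another cause might not.

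This shows how the rules interact. It is not an estimate of how many episodes occurred.

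**The case against.** **On relatedness.** The title prints its own grouping, the error is in the inclusive direction, the all-AE tables are unaffected, and subject listings are planned. All of that stands. A reader might infer that the table misses the events to which the halting rules refer. It does not: it contains them and fails only to isolate them. Nor do those rules run off this table; section 15.3 has the PI monitor accruing safety data against them. Altering the table would also change an output already delivered to the DSMB, so the remedy has to be an addition.

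**On calcium.** Section 7.10.4 can fairly be read as the specific rule for an intended drug effect, consistent with an AE having to be untoward. Section 8 requires every clinical laboratory result to be evaluated and the evaluation documented, so an emergency referral could have been recorded by that route. Symptoms are AEs under either rule. A reader might infer that hypercalcaemia episodes went unrecorded. The documents do not show that; they show only that 7.10.4 did not require it.

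Nor is calcium hidden. It is a secondary endpoint, protocol section 4.5.4 has dosing decisions recorded with their laboratory values, and SAP 7.4.2.5 plots each subject's plasma calcium alongside PTH dose. Those plots give no counts, however, and do not show which AE rule was used. SOP 16 or the DSMB listings may settle the matter, but neither is available here.

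Finally, SAP section 9 says weaning began once enrolment ended in June 2015. Reconciling the text now cannot change how events were collected, only how they are reported.

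**Conclusion.** Both conflicts stand as reporting points that should be corrected.

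The SAP's related count is not the protocol's: it is at least as large, and no listed table gives the protocol-defined number. For calcium, the documents in hand support two rules without saying which governs. Under 7.10.4 read alone, asymptomatic hypercalcaemia that led to suspension or emergency referral need not be an AE if it resolved within 4 weeks.

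The size of each effect in this trial is unknown. The documents give no count of high calcium values, suspensions, referrals or Unlikely gradings. The calcium point assumes that nothing in SOP 16 or the DSMB outputs already fixes the rule. The 9 to 14 rechecks rest on an assumed repeat interval, and the conclusion does not depend on them. A claim that safety events were missed or under-reported would go beyond the documents.

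**What to change.** 1. Leave the tables already given to the DSMB as delivered. For the publication, add a related-AE table limited to Possible, Probable and Definite, with Unlikely shown separately. Appendix 24.1 section 3.1 has the relationship to the product captured on the CRF, so no new data are needed.
2. Reconcile protocol section 7.10.4, section 8, Appendix 24.1 section 3.2 and Appendix 24.10, and state in the report which rule was applied to calcium. No threshold or clinical rule is proposed here.
3. Under SAP section 8, add one supplementary table for the Safety Population subjects who received hPTH, with cohort 1 separate and cohorts 2 and 3 combined:
   - Count each subject once, by highest recorded calcium from first hPTH dose to the start of weaning, including temporary suspensions and whatever the duration.
   - Use the algorithm's own bands. Its rows 11.0–11.9 and above 12.0 leave exactly 12.0 in neither, so show such values on their own line.
   - For each band, give the number of subjects with a recorded hypercalcaemia AE.
   - Add recorded suspensions and emergency referrals, duration of hPTH exposure (time on drug varied), and a note on the completeness of local-laboratory values.

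The cost is two added tables and a short statement in the report. Between-visit calcium comes from local laboratories, and the documents do not say that all of it is in the database in analysable form. If it is not, the table should cover what is held and say so. Reported hypercalcaemia may rise.
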